1. ABSTRACT

BACKGROUND

Prolonged adult obesity is a consistent predictor of major chronic disease risk, including diabetes, heart disease, stroke, and hormone-related cancers. The traditional government-recommended approach to weight loss for obese patients has been calorie-counting / portion control (CC). In 2011 the government began recommending the MyPlate approach (MyP). The CC condition asks overweight patients to reduce their daily calorie intake to less than a recommended calorie target. The MyP approach also limits daily calories but emphasizes eating MORE high-satiety/ high-satiety foods by making ½ of daily food choices minimally processed fruits and vegetables, and ¼ of daily food choices whole grains. The relative effectiveness of the MyP approach compared to the CC approach has not been clinically tested to date in urban, low-income populations.

OBJECTIVES

We propose a randomized controlled trial comparing the patient-centeredness and efficacy of the CC and MyP approaches. MyP uses progressive goal-setting to facilitate a doubling of usual fruit and vegetable intake. To facilitate adherence, both approaches also include changes in the home environment to make healthier choices easier choices. Both conditions encourage patients to do 150 minutes of moderate to vigorous physical activity a week.

Specific Aims

Aim #1. Use qualitative information from patients and clinicians to revise proposed intervention materials and procedures.

Aim #2. Use results of a pilot test of the intervention conditions to revise intervention materials and procedures.

Aim #3. Conduct a 12-months randomized controlled trial involving two home visits, two group education classes, and 7 telephone support/ lifestyle change coaching calls in both conditions.

Aim #4. Obtain qualitative data from providers and coaches; combine with patient survey data to assess intervention feasibility, acceptability and perceived usefulness.

Aim #5. Disseminate results and recommendations to stakeholder groups.

METHODS

Study participants are 261 overweight or obese patients with a BMI range of 27.0-40.3, low-income, mostly Latino and African American adult patients attending community health centers in Long Beach, California. The MyP and CC interventions will be implemented by trained community lifestyle change coaches (promotoras) with brief support from clinicians.

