
While both the DPP and DASH dietary approaches have been shown to reduce excess body weight in the short run, the ability of patients to maintain these approaches for the long-term remains to be determined. Several steps were taken to ensure that the intervention effects for the MyP condition would be long-lasting.

Additional steps incorporated in the current proposal to ensure sustainable intervention impact.

We will take several steps to ensure that the intervention effects for the MyP condition would be sustainable by the community clinics. One step is to replace the masters or doctoral-level health

Patterned after protocol published online in association with Appel et al. (2011)¹⁵

educators/counselors typically used in behavioral weight loss interventions³² with trained community health workers (promotoras). The social modeling of Social Cognitive Theory^{33,34} and experience³⁵ suggest that the predominantly low income Latino immigrant patient population comprising the study population can relate to non-college-educated Latino community health workers better than they can to bilingual but non-Latino masters or doctoral-level counselors.³⁵ African American type 2 diabetes patients as well as Latino patients have benefited from use of community health workers as behavior change agents.^{36,37} On the other hand, community health workers need substantially more training and supervision to carry out the intervention according to protocol. Substantial time is devoted in Year 1 of the present proposal to the training of the community health workers. The Intervention Director's primary responsibility during the active intervention phase is to supervise the community workers in the MyP condition weekly, monitor their lifestyle coaching, and provide guidance as needed to ensure adherence to the MyPlate.gov messages. TCC nutritionists will supervise the community health workers weekly in the CC condition to ensure good adherence to the CC intervention protocol. The use of coaches with closer community ties to the participants holds promise for more sustained lifestyle behavior change benefit.^{36,38-40}

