¹ Accrual took longer than expected. Planned subgroup analyses by sex and ethnicity requiring the original sample size were obviated by the recruitment of fewer men than anticipated (4.6% versus 30% expected) and fewer African Americans than expected (7.7% versus 15% expected). Statistical power for remaining planned subgroup analyses involving women and Latinos exceeded 80% at the lower sample size of N =261.

Patterned after protocol published online in association with Appel et al. (2011)¹⁵

enrolling mostly women. Randomization will occur at the individual level despite the risk of patients assigned to different conditions talking to each other in the waiting room and discovering that their health coaching messages are different. Except for brief encounters with trained clinical staff about their participation in the lifestyle change coaching program, most of the health information transmitted in this program will occur in the home, by phone or in group education classes, not in the examination room. Analyses will take into account the fact that patients are nested within clinics and within providers but previous experience with randomization at the clinic level convinced us that the study design was stronger, easier to administer and easier to analyze when randomization occurred at the level of the individual patient instead of at the level of the primary care clinic.

The Community Advisory Board. The Community Advisory Board (CAB) is comprised of members representing all major stakeholders: UCLA investigators, TCC investigators, TCC patient representatives, community public health leaders, thought leaders in lifestyle change interventions. The CAB can be viewed as equivalent to the Board of Directors. Members' input will help shape the design of the proposed research, interpretation of results and the nature of the final recommendations, but will generally leave the day-to-day decision-making to the TCC and UCLA investigators. Members with equivalent ability to represent specific stakeholders with respect to community approaches to weight control will be selected to replace those who can no longer serve on the CAB, with the objective of continuing to represent fairly the full range of stakeholders. Study investigators are part of the CAB because their presence validates the stated authority of the CAB to make decisions about study implementation, interpretation of results and final recommendations.

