Randomization procedure. If all screening and baseline measures indicate that the patient remains eligible, a programmed application in REDCap generates a random assignment to experimental condition for the patient at the end of the screening assessment. The lifestyle change coaches can look up in REDCap's database the study participants assigned to their condition. The coach will then call the patient and arrange for the first coaching session, if appropriate. The research assistants will be kept ignorant of the patient's assignment to experimental condition, to reduce the chance for bias. Of necessity, the lifestyle change coaches will be aware of the patient's experimental assignment but will be instructed to follow the protocol carefully, so as not to introduce any personal bias.

The REDCap data entry system has also been programmed to generate a randomly determined assignment to condition, if the would-be participant met all inclusion criteria and reported no exclusion criteria. Hence, at the completion of the screening visit the study participant will be informed about the experimental condition that he/she had been assigned to and the name and contact number of his/her lifestyle coach. More information about the randomization process is provided below.

Follow-Up (FU) Visits: Participants will be asked to attend in-person follow-up visits at 6 and 12 months after randomization. Most of these data will be collected in-person at the clinic but the FFQ may be administered over the phone, depending on the time constraints of the study participant. The target windows used to schedule participants will coincide with a one month period around the 6 and 12 months follow-up visits. During follow-ups, we will also ask patients to evaluate the trial, including their perceptions of the acceptability and usefulness of the intervention and its components (MyPlate or Calorie Counting).

Measurement intervals.

Most measures will be assessed at baseline, at 6 months and 12 months follow-up. The Block Food Frequency Questionnaires will be administered only at baseline and 12-months follow-up, not at 6-months follow-up, to minimize the burden on study participants. Questionnaires were administered in the order described below in Table 4.

Table 4: Data Collection Items and Schedule by Contact

	Screening	Baseline	F-up-6	F-up-12
Eligibility/Interest	X			
Informed Consent	X	X		
Weight (self-reported)	X			
Height (self-reported)	X			
Weight (measured)		X	X	X

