13. STATISTICAL POWER AND SAMPLE SIZE ESTIMATION

Hypotheses for the Two-Group Randomized Control Trial Design: The aim is to conduct an RCT of the impact of CC versus MyP on patient-centered outcomes in up to eight community clinic sites in Long Beach. Participants will include: 150 patients randomly assigned to receive

Patterned after protocol published online in association with Appel et al. (2011)¹⁵

CC from trained health coaches, another 150 patients assigned to receive MyP from another group of trained health coaches over the course of 12 sessions in six months.

Intervention check: Does exposure to MyP versus CC lead to increased patient reports of fruit and vegetable intake in MyP? A preliminary check will be made to confirm that one of the defining features of the MyP approach, namely a doubling of F&V intake, was reflected in study participants' daily intake of F&V assessed at follow-up. If no difference were observed in F&V assessed at follow-up then the validity of the experimental contrast would be jeopardized. There could still be experimental effects, but the causal mechanisms would be unknown. Because numerous studies have succeeded in getting patients to double their intake of F&V for up to four years, a negative outcome of this intervention check is unlikely.²⁵

Question: Does exposure to MyP versus CC lead to decreased patient 12-months reports of daily hunger ratings/ daily meal satisfaction ratings/ daily fullness ratings in MyP during a time when patients were trying to lose excess weight (primary)? Will exposure to MyP versus CC lead to increased patient weight control self-efficacy, patient quality of life and patient satisfaction with her/his weight control program (primary)?

Question: Will exposure to MyP versus CC lead to increased weight loss/ reduced waist circumference equally for both conditions sustained for 12 months (secondary)?

Avoidance of bias. Covariates and effect modifiers. Standard demographic variables, including gender, age, ethnicity, marital status, and educational attainment will be included as covariates. Possible effect modifiers will also be included as covariates, including language preference (English / Spanish), last month food security, meal-skipping status, and daily physical activity level.

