Sample size. (3) Statistical power. We power this proposal for the two-group (MyP vs CC) randomized design, setting alpha at 0.025 in order to have an experiment wise type I error rate of 0.05 after testing two hypotheses. Test of hypothesis #1 is therefore a test of the effect of MyP versus CC on the 12 months report of freedom from hunger measure used in the trial most similar to the trial proposed here.¹⁸³ The intervention effect size reported by Ello-Martin and associates is Cohen's $d = .52$. (Cohen's Effect Size = $(53.5 - 46.7) / 13.2 = .52$). The total sample sized needed to detect this effect, given a two-tailed critical $P = .025$, minimum statistical power of .80, and $\rho = .85$ the total sample size needed is approximately $N = 144$. The test of the second hypothesis is a test of MyP versus CC on the body weight lost over 12 months. We have three sources to draw on for estimating effect size involving weight loss over 12 months. The first is Ello-Martin and associates, whose low-fat, high fruit and vegetables intervention²⁰ was similar to but not identical to the DASH diet + (sat. fat & sugar restriction) featured in the current proposal.¹⁶ Ello-Martin's DASH-similar + fat restricted diet yielded a 12-months weight loss of 7.9 kg (SE=0.9, n=35) whereas the fat restriction-only condition yielded a 12-months weight loss of 6.4 kg (SE = 0.9, n=36). The total sample size needed to detect a similar 12-months weight loss difference at $\alpha=0.025$, $\text{power}=0.80$, $\rho = .7$ is $N= 206$ ($n=103$ per group). In Appel's recent clinical trial¹⁵ the in-person DASH-like dietary intervention yielded a 5.4 kg (SE=0.7, n=124) weight loss relative to baseline at 12 months follow-up.¹⁵ The body weight lost in response to Wadden's DPP-like dietary intervention¹⁴ was 3.4 kg (SE=0.6, n = 112) at 12 months follow-up¹⁸⁴ By design the protocols followed by Appel et al. (2011) and by Wadden et al. (2011) were similar, so comparing means across these two studies is informative. The sample size needed to detect this difference at 12 months at $\alpha = 0.025$, $\text{power}=0.80$, $\rho = .7$ is $N = 270$ ($n = 135$ per group). Based on the best available sources in the literature for information about reasonable estimates of the effect size to be expected and given an expected attrition of 20% at 6 month follow-up, the baseline initial sample of 300 (N=300 for 2 groups) appears to provide ample statistical power for the two experimental comparison hypotheses

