14. ANALYSIS PLAN

General. After the data have been cleaned, we will examine the distribution and dispersion of data through descriptive numerical summaries and graphical tools such as scatter plots and box plots, probability plots, scatter matrix plots, co-plots, and trellis graphics to assess distributional assumptions and relationships among important variables. Before attempting a longitudinal analysis of the change in our outcomes using a linear mixed model, we will use profile plots, empirical summary plots and correlograms to guide us in the formulation of our model.¹⁸⁵ Some data will be subjected to scale transformation (e.g., logarithmic), as needed, to meet statistical assumptions. Box Cox or Yeo-Johnson transformations may also be used for this purpose.

Because missingness can potentially spoil or invalidate a study, we will spare no effort to minimize incomplete or missing data. All data will be carefully inspected to identify missing items, outliers, or other influential features. We will strive to form conclusions that are robust to different missing-data mechanisms,¹⁸⁶ and we will consult with colleagues in the Fielding School of Public Health Biostatistics Department regarding the use of incomplete-data analysis strategies that make effective use of available information.

Preliminary analyses will compare treatment groups on descriptive and clinical characteristics at baseline to ensure that randomization has succeeded. SAS (PC version 9.3) and Stata (Intercooled version 13) comprehensive database management and statistical packages will be used for descriptive calculations, group comparisons, and conditional regression modeling.

Experimental contrasts will be examined *a priori* using Stata's mixed effects modeling procedures, with standard errors corrected for the effects of clustered data.¹⁸⁷ It is known that even with randomized designs, covariate imbalance between treatment groups can exist and threaten the integrity of the design.¹⁸⁸ Because the potential bias may result in misleading conclusions, we will perform a thorough examination for covariate imbalance. Specifically, we will examine the distributions of all important variables at baseline and at the major endpoint (12 months follow-up), and also at intermediate points if the covariate is time-varying. Formal statistical methods for testing selection bias (systematic baseline imbalances) based on response data will be followed.^{188,189}

Missing and incomplete data

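### Coaches are nested in arm, but the plan names only clinic and provider as cluster levels and the sample size allows for no clustering

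*Combined protocol and SAP*

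**What the plan says.** **Coaches and arms.** Section 13 describes 150 patients receiving CC from trained health coaches and "another 150 patients assigned to receive MyP from another group of trained health coaches". The randomisation procedure in section 8 (repeated in section 10) fits this: "The lifestyle change coaches can look up in REDCap's database the study participants assigned to their condition". Supervision is also split. Section 3 says "TCC nutritionists will supervise the community health workers weekly in the CC condition", while the Intervention Director supervises the MyP coaches.

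**Cluster levels.** Under the choice of study design, section 4 states "Analyses will take into account the fact that patients are nested within clinics and within providers" and places randomisation at the individual patient. Section 14 plans mixed-effects models "with standard errors corrected for the effects of clustered data" and gives no level. The covariate list in section 13 has no coach term.

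**Sample size.** Section 13 works by "setting alpha at 0.025 in order to have an experiment wise type I error rate of 0.05 after testing two hypotheses". It gives effect sizes, power and correlations, but no ICC, cluster size or design effect. The number of coaches is not stated anywhere.

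**The concern.** The coaches deliver the treatment: up to 11 contacts by home visit, phone and group class. Section 4 itself notes that little of the health information passes in the examination room. If some coaches get better results than others, patients of the same coach have correlated outcomes.

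Clinics and primary care providers each have patients in both arms, so their effects largely cancel in the arm difference. Coach effects do not cancel, because no coach serves both arms. The mean coach effect in MyP minus the mean coach effect in CC becomes part of the estimated treatment difference, and its variance falls only as coaches are added, not patients.

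An analysis without that variance component would give intervals that are too narrow and more than the planned share of false positives. An apparent advantage for MyP could then partly reflect who was hired to deliver it, which bears directly on the trial's question of which approach clinics should feature.

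**Working it through.** **1. The plan's own figure (hunger, section 13).** Inputs: two-sided alpha 0.025 (z = 2.2414), power 0.80 (z = 0.8416), d = (53.5 − 46.7)/13.2 = 0.515, rounded to 0.52.

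n per arm = 2(2.2414 + 0.8416)²/d²

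- d = 0.52: 70.3, so 71 per arm and 142 in total.
- d = 0.515: 71.7, so 72 per arm and 144 in total.
- d = 0.52 with the noncentral t: 72 per arm and 144 in total.

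The stated 144 is therefore an independent-patient calculation, with nothing in it for clustering.

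**2. Assumptions that the documents do not supply.**

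- Completers: 261 × 0.80 = 209. Section 13 states the 20% attrition for 6 months; applying it at 12 months is an assumption.
- Coaches per arm: k = 3 to 6, with k = 2 as a further case.
- Coach ICC: 0.01 to 0.05.

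**3. Formulas.**

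- Patients per coach: m = 209/(2k)
- Design effect: DE = 1 + (m − 1) × ICC
- Real error of a nominal 0.025 test that omits coach: 2[1 − Φ(2.2414/√DE)]
- Noncentrality: δ = 0.52/√(4·DE/209)
- Power, normal approximation: Φ(δ − 2.2414)
- Power, conservative: noncentral t with noncentrality δ on 2(k − 1) df, two-sided 0.025

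With coach left out, DE = 1, δ = 3.759 and power = Φ(1.518) = 93.5%.

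**4. Results.**

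| Coaches per arm | ICC | m | DE | Real error | Power, normal | Power, t on 2(k − 1) df |
|---|---|---|---|---|---|---|
| 6 | 0.01 | 17.4 | 1.16 | 0.038 | 89% | 79% |
| 4 | 0.02 | 26.1 | 1.50 | 0.067 | 80% | 57% |
| 3 | 0.05 | 34.8 | 2.69 | 0.17 | 52% | 27% |

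Worst row in full: DE = 1 + 33.83 × 0.05 = 2.69; 2.2414/√2.69 = 1.366, so the error is 0.17; δ = 2.291, so normal power is Φ(0.050) = 52%. The t critical value on 4 df is 3.495, which gives 27%.

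In the middle row, two tests at 0.067 sum to about 0.13, against the intended 0.05. With 2 coaches per arm the real error is 0.068 (ICC 0.01) to 0.235 (ICC 0.05).

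**5. Does adjusting for clinic absorb the coach effect?** A simulation of 10,000 runs used 208 patients and two clinics, with clinic in the model and coach left out. With 4 coaches per arm, rejection at nominal 0.025 was 0.022, 0.068 and 0.136 for ICC 0, 0.02 and 0.05. With 2 coaches per arm it was 0.028, 0.117 and 0.236. Adjusting for clinic does not remove the excess, and at ICC 0 there is none to remove.

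**The case against.** **The analysis may already cover coach.** A reader might infer that the planned analysis ignores coach. The documents do not support that: the clustered-data clause in section 14 names no level, so it neither includes nor excludes coach. What stands is that the only levels named anywhere are clinic and provider. Provider does not naturally include coach, since the aims in section 1 list the two separately ("Obtain qualitative data from providers and coaches"). Only for the sample size is it exact to say that clustering is ignored.

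**The coach ICC may be near zero.** Section 11 has features meant to limit differences between coaches: certification, leader guides, computer-driven call content, observed contacts and weekly meetings with corrective feedback. These could make the ICC small but do not show that it is zero. The inflation is therefore conditional. At the mild end above it is modest: error 0.038, and 89% power by normal approximation.

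**The remedy can cost a lot of power.** This stands. A reader might take 52 to 89% as the power of the corrected analysis, but that range keeps a normal critical value and is an upper limit. On 2(k − 1) df, a model with coach has about 63% power with 3 coaches per arm and 31% with 2, even if the true ICC is 0. Satterthwaite or Kenward-Roger may allow more df than this conservative limit.

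**Coach data may not be held.** A reader might infer that REDCap stores a coach for each patient. Section 8 says only that coaches can look up the participants in their condition and that participants are told their coach's name. That suggests a designated coach, but no section says that the link is stored, or that one coach delivers all the contacts.

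**Conclusion.** The concern holds in conditional form. Coach is nested in arm by design, is not named as a cluster level, and has no place in the sample size. For any positive coach ICC, clustering only on clinic and provider understates the standard error of the arm difference and takes the per-test error above 0.025.

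The direction is firm, but the documents cannot fix the size. The range given (design effect 1.16 to 2.69, real error 0.038 to 0.17) rests wholly on the assumed completers, coach numbers and ICCs. On the same assumptions, power for the hunger effect is at most 52 to 89%, and about 27 to 79% at the conservative df limit, against 93.5% with coach left out.

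It would go too far to say that the stated alpha is certainly not kept: with ICC 0 it is, and the cluster level in section 14 is open. This should be corrected in the plan, but it does not show that the trial's conclusions will be wrong.

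**What to change.** 1. In section 14, name coach, nested in arm, as a cluster level in the mixed model for the MyP versus CC contrast, with Satterthwaite or Kenward-Roger degrees of freedom, if the number of coaches supports it.
2. If it does not, report the primary interval under a range of fixed coach ICCs (for example 0.01, 0.02 and 0.05) as a sensitivity analysis, multiplying the standard error by √DE. With 4 coaches per arm and 209 completers the multipliers are 1.12, 1.23 and 1.50.
3. State the number of coaches per arm, and decide between 1 and 2 before outcomes are compared by arm.
4. Record the coach assigned to each participant. The name given at the end of screening defines this even for people who attend no session, so it suits the intention-to-treat analysis.
5. Restate the section 13 power over a range of coach ICCs at the existing N. Footnote 1 in section 4 reports accrual as past, with 261 participants, so the restatement informs interpretation and does not change the sample size.

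The cost is a few sentences of plan text, one model term, and confirming or rebuilding the link between coach and participant. The real downside is wider intervals and a less favourable power statement, which can be substantial with few coaches per arm.
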